9.1 Safety and Efficacy Endpoints

Assessment of early clinical outcomes in focal SBRT for low risk prostate cancer patients. Twenty-four hormone naïve low to intermediate risk prostate cancer patients will be screened for PSA level, acute toxicities and quality of life (QOL) measures at baseline and twelve will be followed at longitudinal follow-up appointments.

Acute and Late GI and GU Adverse Events (AEs)

Adverse events are evaluated by the CTEP Active Version of the NCI Common Terminology Criteria for Adverse Events (CTCAE). We will record in Oncore the highest grade reported during a reporting period. The treatment-related attribution includes definitely, probably or possibly related to treatment. An acute adverse event is defined as the first occurrence of worst severity of the adverse event ≤ 30 days after the completion of RT. We will evaluate the acute radiation therapy-related adverse events. Specifically, we are interested in the percentage of acute GI and GU Grade 3+ adverse events that may occur, which is considered to be similar to the high RT dose arm of RTOG 0126 in terms of RT dose. If our partial prostate hypofractionated regimen has an acceptable percentage, then it will be deemed to have an acceptable adverse event profile. We will report the percentage for the regimen as well as the one-sided 97.5% confidence interval. For example, the number of patients in the high dose arm of RTOG 0126 Phase II reported that 1% of patients experienced Grade 3+ GI/GU acute toxicity, with no patient experiencing Grade 4 or 5 toxicities (citation) should be greater than this pilot study. A late adverse event is defined as the first occurrence of worst severity of adverse event > 180 days after RT completion. Late Grade 3+ GU/GI toxicity information will be collected and reported also.

PSA Failure

Failure occurs when the PSA is first noted to be 2 ng/mL or more than the patient's nadir value post RT completion (Phoenix, Abramowitz 2009). PSA failure at 6, 12 and 24 months following RT will be estimated for the series by the cumulative incidence method (Gray 1988). Also, confidence intervals will be reported.

Disease-Free Survival (DFS)

The disease-free survival duration will be measured from the date of treatment to the date of documentation of disease progression or until the date of death from any cause. DFS at 6, 12 and 24 months for each patient and the series by the Kaplan-Meier method (Kaplan 1958). Also, 95% confidence intervals will be reported.

Analysis for Endpoints Related to HRQOL

We will use three instruments to measure HRQOL: the Expanded Prostate Cancer Index Composite (EPIC), the Utilization of Sexual Medications/Devices, and EQ-5D. Protocol eligible patients will be included in the HRQOL analysis only if they have provided baseline and at least one subsequent measurement. All HRQOL instruments (EPIC, the Utilization of Sexual Medications/Devices and EQ-5D) will be collected on all cases participating in the trial. The standard departments QOL instruments may also be used to report outcomes with both the International Prostate Symptom Score (IPSS) and Sexual Health Information Measurement (SHIM) obtained from chart review.

The EPIC Supplement Utilization of Sexual Medications/Devices, and EQ-5D will be collected at pretreatment (baseline) and at 6, 12 and 24 months after radiation therapy ends. Patient self-assessment of symptoms will be performed using four primary EPIC scales: urinary, bowel, hormonal and sexual symptoms. The Utilization of Sexual Medications/Devices and EQ-5D Questionnaires are found in Appendix 3.

For all primary HRQOL analyses we will estimate the degree of change from baseline to 6, 12 and 24 months as continuous variables. For this endpoint, in each domain, the actual change score will be used as the statistic and a t-test will be used to evaluate if the change is different from 0. Confidence intervals also will be computed

The primary objective in HRQOL analysis is to estimate the change from baseline to 24 months. The response will be the change of measurement from baseline to 24 months (or the last available HRQOL data point where data are missing). The one-sample t-test will be used to test the null hypothesis that response change is 0. For the regimen to maintain the overall significance level for testing three HRQOL instruments. In addition, we will describe the distributions of HRQOL data collection patterns over all collection points in each treatment arm.

Demonstrate dosimetric and biological advantage of focal SBRT versus whole-gland therapy
Treatment plans from focal versus simulated whole-gland SBRT for each patient will be compared for target volume size, dose distribution, and dose reduction to organs at risk (OAR). Additional assessments for planning volumes based solely on imaging versus with correlated histopathology to define PTVs will be collected, evaluated and reported. Biological modeling will be used to evaluate tumor control probability and normal tissue complication probability (NTCP) between the two treatment paradigms (focal versus virtual simulation of whole gland treatment using conventional treatment per institutional standards). Standard independent methods of dosimetry calculations will be evaluated by Medical Physics staff and reported by Medical Physics co-investigators, utilizing such programs as Pinnacle and MUcheck, and Monte Carlo simulations. Subject data sets appropriately de-identified by a study co-author may be additionally evaluated utilizing advanced software MRI analysis for predictive modeling and comparison to tumor volume selection as identified with histopathology validation.

We estimate that 12 patients will be treated on study, and that 24 patients may be screened. MRI and histopathology data will be collected for all patients consented to the study and screened.

Interim Reports to Monitor Study Progress

Patients will have imaging sessions (MRI and CT Simulation) for treatment planning and delivery of radiation therapy. Interim imaging reports will be provided to the funding partners following the first 3-6 subjects screened, along with case study descriptions, and limited de-identified treatment plan screen shots along with composite image sets. Other interim reports will evaluate workflow and carepath processes.

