9.2 Effectiveness Assessments

Clinical information from subjects will be recorded onto Case Report Forms and subsequently transferred into OnCore. Patients who additionally consent to a separate Urology Registry will have their data added to the Urologic Oncology & Minimally Invasive Therapies Database for UHHS Faculty.

Should any unanticipated adverse events occur during the course of the study, the clinical research coordinator will ensure that they are documented by the investigator and reported to the appropriate Institutional Review Board per its then-current guidelines. If the determination is made that an unanticipated adverse event presents an unreasonable risk to subjects, the clinical evaluation will be paused, or if deemed appropriate (to enable further investigation), the subject will be withdrawn as soon as safely possible.

Adverse events, grade 3 and above, will be captured in OnCore and will be reported in accordance with the Data and Safety Monitoring Plan (DSMP) that is approved by the Cancer Center Protocol Review and Monitoring Committee (and aligned with the NCI-approved plan).

Antitumor Effect – Solid Tumors

For the purposes of this study, subject PSA, DRE and PSA data will be recorded in Oncore as evaluations for response to radiation therapy, per standard of care procedure during post radiation therapy follow-up visits. In addition to PSA and DRE evaluations, RECIST (v.1.1) measurements will be acquired using mpMRI surveillance. Response and progression will be evaluated in this study using the new international criteria proposed by the revised Response Evaluation Criteria in Solid Tumors (RECIST) guideline (version 1.1) [Eur J Ca 45:228-247, 2009]. Changes in the largest diameter (unidimensional measurement) of the tumor lesions and the shortest diameter in the case of malignant lymph nodes are used in the RECIST criteria. We will also analyze volumetric response to therapy based on serial MRI data that will be evaluated using radiation oncology treatment planning computers.

Definitions

Evaluable for toxicity All patients will be evaluable for acute toxicity within 90 days from the time of the end of the course of radiation therapy.

Evaluable for objective response

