10.2 Statistics

Statistical Considerations

Chi-square and cluster re-sampling analyses will be used to correlate suspicion on multiparametric magnetic resonance imaging and the incidence of cancer detected on biopsy.

The primary goal of this study is to evaluate acute and late toxicities. In addition clinical data will be collected to monitor for tumor control. Digital rectal examination (DRE) and serum prostate antigen (PSA) will be evaluated every 3 months for two years. Toxicity will be evaluated EPIC EQ D5, Sexual Medication, Device Screening Questionnaires completed by the patients or in conversation with the patient by the clinical staff, at baseline, 6, 12 and 24 months following the end of radiation therapy (+/- 14 days). Rates of acute and late side effects and adverse events will be summarized as proportions, with 95% confidence intervals.

Biochemical failure will be based on PSA values using the Phoenix definition (clinical nadir +2ng/mL). Data from all patients will be pooled. Survival rates estimated from the Kaplan-Meier curves will be estimated with 95% confidence intervals. We will also track virtual treatment plans based on standard models for treatment to the whole gland versus partial gland MRI-TPUS validated planning to report change in dosimetric parameters of the focal SBRT versus traditional whole-gland treatment plans for statistical comparison.

Either a positive DRE or rising PSA may be used as clinical indication for additional MRI surveillance. When additional MRI are available, tumor volume will be summarized by mean \pm STD and the difference between two time points (pre and post treatment) will be examined using paired T-test. Radiographic efficacy will be summarized by calculating Kaplan-Meier curves for the following: disease-free survival, time to local progression, time to distant failure. Descriptive reports of RECIST (1.1) and volumetric findings will be provided.

Acute/Late Toxicity and Quality of Life Measurements

Using multivariate analysis, we will report acute and late (>180 days post SBRT) rates of GI toxicity with dose-volume histogram. We will also report time to event analyses collected for all available HRQOL data collected.

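### Acute (to day 30) and late (after day 180) toxicity windows leave days 31–180 outside every planned CTCAE rate

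*Combined protocol and SAP*

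**What the plan says.** Section 9.1 (Acute and Late GI and GU Adverse Events) defines an acute event by "first occurrence of worst severity of the adverse event ≤ 30 days after the completion of RT" and a late event by "first occurrence of worst severity of adverse event > 180 days after RT completion". It plans the percentage with acute Grade 3+ GI/GU events, with a one-sided 97.5% confidence interval, and says late Grade 3+ events will also be reported. An acceptable acute percentage is to mean an acceptable adverse event profile. On recording, it says "We will record in Oncore the highest grade reported during a reporting period".

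Section 9.2 (Definitions) uses a different period: "All patients will be evaluable for acute toxicity within 90 days from the time of the end of the course of radiation therapy". It also states that "Adverse events, grade 3 and above, will be captured in OnCore".

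Section 10.2 says "The primary goal of this study is to evaluate acute and late toxicities", that "Rates of acute and late side effects and adverse events will be summarized as proportions, with 95% confidence intervals", and, under Acute/Late Toxicity, that "we will report acute and late (>180 days post SBRT) rates of GI toxicity with dose-volume histogram". It does not restate the acute window.

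The calendar in 7.3 has adverse events assessed at 30 days, 3 months, 6 months and each later visit.

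**The concern.** The two windows do not meet. An event that reaches the counted grade only between day 31 and day 180 is neither acute nor late, and no third category or any-time rate takes it in. The data will exist, since the 3-month visit and much of the run-up to the 6-month visit fall in this period, but the plan gives those events no place in a toxicity proportion.

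Section 10.2 makes toxicity the primary goal (9.0 names MRI–histopathology correlation instead, with EPIC co-primary endpoints), and the hypothesis in 2.0 includes less toxicity than whole-gland treatment. A report that followed the plan could show no acute and no late Grade 3+ events although a patient had one.

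The dating rule may widen the gap. If an event is dated by its overall peak, one already at Grade 3 by day 30 that worsens in days 31–180 leaves the acute rate as well.

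**Working it through.** The plan states no figure for this period, so there is none to reproduce. The check compares the windows and then sizes the effect.

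**Inputs from the documents**
- Acute: up to day 30 after RT (9.1).
- Late: after day 180 (9.1, repeated in 10.2 for the GI dose-volume report).
- Acute evaluability: 90 days (9.2).
- Treated patients: 12 (4.2, 9.1, 10.2).

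**Length of the gap**
- Under 9.1: days 31 to 180, 180 − 30 = 150 days, or 150/180 = 83% of the first 180 days.
- With 90 days from 9.2 as the acute limit: days 91 to 180, 180 − 90 = 90 days.

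**Where an event is counted under 9.1**

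| Event history | Dated by overall peak | Worst grade within each window |
|---|---|---|
| Grade 3+ only by day 30 | acute | acute |
| Grade 3+ only in days 31–180 | neither | neither |
| Grade 3 by day 30, Grade 4 in days 31–180 | neither | acute |
| Grade 3+ only after day 180 | late | late |

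The second row is lost on either reading. The third depends on the reading. The reporting-period sentence in 9.1 favours the right-hand column, but the text does not settle it.

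**Effect on the proportion** (exact Clopper-Pearson limits, n = 12; one patient is 1/12 = 8.3 points)

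| Patients counted | Rate | Exact 95% CI |
|---|---|---|
| 0/12 | 0% | 0–26.5% |
| 1/12 | 8.3% | 0.2–38.5% |
| 2/12 | 16.7% | 2.1–48.4% |

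The 0/12 upper limit is 1 − 0.025^(1/12) = 26.5%. The one-sided 97.5% upper limit planned in 9.1 equals the upper limit of the two-sided 95% interval. If nobody is counted as acute or late and one patient has an event confined to the gap, the planned rates show 0/12 and the any-time rate is 1/12. If one patient is counted and another has such an event, the contrast is 1/12 with 2/12. The acute rate and its limit change only if the acute window itself is lengthened.

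**Chance that it happens.** The documents give no risk for this period, so p is assumed: the per-patient risk of a Grade 3+ GI/GU event confined to days 31–180 in a patient counted in neither rate. P(at least one of 12) = 1 − (1 − p)^12.

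| Assumed p | 1% | 2% | 5% | 10% |
|---|---|---|---|---|
| P(at least one) | 11.4% | 21.5% | 46.0% | 71.8% |

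**The day-180 edge.** This point is secondary and conditional. Six months is about day 182. If the ±14 days that 10.2 gives for questionnaires also applied to the adverse event assessment at that visit, the visit could fall on days 168 to 196, which is 29 days. If events then took the visit date, 13 of those days (168–180) would be unassigned and 16 (181–196) late. The general visit window in 7.0 has no unit and does not help.

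**The case against.** The strongest reply is that nothing is lost and no decision depends on it. Grade 3+ events go into OnCore, 6.2 has side effects recorded on case report forms without a day limit, related Grade 3–4 events reach the IRB through expedited or continuing review, and IPSS, SHIM and EPIC cover part of the period. No numerical limit is attached to the acute percentage. The limits that do exist, for EPIC bowel and urinary change in 9.0, are untouched. Section 10.2 describes a pilot not powered for toxicity, and the plan never says that the acute and late rates together are exhaustive. All of this stands and limits the consequence. None of it supplies a CTCAE rate for days 31–180.

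The sentence in 10.2 on rates could be parsed so that adverse events stand apart from acute and late side effects and include all of them. That reading is loose, and no such rate is defined.

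The wording in 9.1 most naturally means the event's own date, so the visit-window calculation shows only what an unstated rule could do. That is fair.

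Finally, the one Grade 3+ GI/GU figure in the documents is 1%, for acute toxicity in the RTOG 0126 high-dose arm, with this regimen expected to be lower. At 1% the likeliest result is no affected patient. That also stands: the higher assumed risks show sensitivity and are not forecasts.

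**Conclusion.** The concern holds: the windows are wrong as written. Under 9.1 and 10.2, days 31–180 belong to no planned CTCAE proportion, and the 90-day wording in 9.2 conflicts with 9.1 without closing the gap. Confidence is high that the gap exists. Its effect is conditional: 8.3 points for each patient omitted, and an 11% to 72% chance of at least one omission across assumed risks of 1% to 10%. Each planned rate is right for its own window; the understatement arises when the two are read together as total toxicity. No stated decision limit is crossed. This should be fixed because the stated rules themselves drop collected events from an evaluation that 10.2 calls the primary goal.

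**What to change.** 1. Reconcile 9.1, 9.2 and 10.2 to one set of contiguous reporting windows, or keep 30 and 180 days and add a day 31–180 category.
2. Count the worst grade reached within each window, so that an event that worsens counts in every window where it meets the grade.
3. Assign events by their actual date, not the date of the visit at which they are found.
4. Report the proportion of patients with any Grade 3+ GI/GU event from the start of RT to 24 months, with an exact confidence interval.
5. State which acute window lies behind the 1% comparator figure before comparing with it; the documents do not say.

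The cost is wording plus one or two more tabulated rates for 12 patients, which may look slightly less favourable. Adverse events are already assessed at every follow-up visit, so no visits are added. The adverse event form must hold an event date if it does not already.

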Temporal pattern of quality of life scores will be summarized graphically; and repeated measures analysis of variance (ANOVA) will be conducted to test for changes in scores over time. The predictive value of demographic, pathological and clinical factors on the scores will be examined by mixed models assuming missing values are missing at random.

Sample Size

Twelve patients will be evaluated in this pilot study. As a proof-of-principle study, it's not design to have the appropriate power (80%) for detecting significant difference in clinic outcomes (i.e.

toxicities, survival or QOL), but to provide some preliminary data for future studies. A sample of 12 patients, however, achieves 78% power to detect 8% difference of urinary toxicity against historical controls under whole gland therapy using a two-sided binomial test with the target significance level of 0.2. We anticipate that a minimum of twenty four patients will be screened leading to twelve patients who will be treated and evaluated on-study in this pilot study.

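### The acute Grade 3+ acceptability verdict has no stated cut-off, and 12 patients cannot support a conclusion against its only yardstick, a 1% rate

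*Combined protocol and SAP*

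**What the plan says.** The endpoint is set in Section 9.1: "we are interested in the percentage of acute GI and GU Grade 3+ adverse events that may occur". The decision follows: "If our partial prostate hypofractionated regimen has an acceptable percentage, then it will be deemed to have an acceptable adverse event profile". No numerical cut-off is given.

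The next sentence promises an interval: "We will report the percentage for the regimen as well as the one-sided 97.5% confidence interval". It does not say which bound is meant, or whether the interval decides acceptability.

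The text then offers, as an example, the high-dose arm of RTOG 0126, which "reported that 1% of patients experienced Grade 3+ GI/GU acute toxicity", and adds that this figure "should be greater than this pilot study".

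Section 10.2 fixes the denominator: "Twelve patients will be evaluated in this pilot study". For the same kind of rates it specifies a different interval: "Rates of acute and late side effects and adverse events will be summarized as proportions, with 95% confidence intervals". Under Sample Size it says of the study that "it's not design to have the appropriate power (80%) for detecting significant difference in clinic outcomes", and it lists toxicities among those outcomes.

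**The concern.** Section 9.1 does more than describe. It commits the trial to calling the regimen's adverse event profile acceptable if an unstated condition is met. Because neither the threshold nor the statistic to be compared with it is fixed, the condition could be settled after the data are seen.

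The one figure offered, 1%, is far below what 12 patients can resolve, since the smallest non-zero percentage they can produce is 8.3%. An event-free series would probably be declared acceptable while remaining compatible with a rate many times the benchmark.

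The matter is not peripheral. Section 10.2 names the evaluation of acute and late toxicity as the primary goal (Section 9.0 names a different one, the mapping role of MRI). Section 19.0 plans publication of acute toxicity, and Section 1.2 sees the pilot as a possible basis for Phase I/II and multi-centre trials.

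**Working it through.** **Inputs from the documents.** n = 12 (Section 10.2, Sample Size); benchmark 1% (Section 9.1, as an example); one-sided 97.5% interval (Section 9.1). All 12 treated patients are taken as evaluable.

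**Assumed for illustration.** True rates of 5% and 10%. The documents name no unacceptable acute Grade 3+ rate.

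**Figure to reproduce.** None. The plan gives no error rate, pass count or pass probability for this decision. The 78% power under Sample Size concerns urinary toxicity against historical controls and is not used here.

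**Step 1: resolution.** 0/12 = 0%; 1/12 = 8.3%. No observed value lies between 0% and 8.3%.

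**Step 2: exact (Clopper-Pearson) one-sided 97.5% limits.**
- Upper limit for 0/12: 1 − 0.025^(1/12) = 26.5%.
- Upper limit for 1/12: 38.5%.
- Lower limit for 1/12: 1 − 0.975^(1/12) = 0.2%.
- Lower limit for 2/12: 2.1%.

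**Step 3: sample size for an upper limit of 1% with no events.** Solve 0.99^n ≤ 0.025: n ≥ ln(0.025)/ln(0.99) = 367.04, so 368 patients.

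**Step 4: three readings of the rule.** With true rate p:
- P(0/12) = (1 − p)^12
- P(0 or 1 of 12) = (1 − p)^12 + 12p(1 − p)^11

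| Reading | Results that pass | Chance of passing, p = 1% | p = 5% (assumed) | p = 10% (assumed) |
|---|---|---|---|---|
| A. Observed percentage not above 1% | 0/12 only | 88.6% | 54.0% | 28.2% |
| B. Upper limit at or below 1% | none | 0% | 0% | 0% |
| C. Fails only if lower limit exceeds 1% | 0/12 or 1/12 | 99.4% | 88.2% | 65.9% |

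For example, at p = 10%, A gives 0.9^12 = 0.282 and C gives 0.282 + 12 × 0.1 × 0.9^11 = 0.659. Under A, a regimen truly at 1% fails 100% − 88.6% = 11.4% of the time.

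**Step 5: interval in Section 10.2.** If its 95% interval is two-sided, exact and equal-tailed, its upper limit for 0/12 is the same 26.5%. If it is one-sided, the limit is 1 − 0.05^(1/12) = 22.1%. The section does not say which.

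**Step 6: which events count.** Section 9.1 defines acute as up to 30 days after radiotherapy. Section 9.2 (Definitions) makes patients evaluable for acute toxicity within 90 days of its end. The numerator depends on which window applies.

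**The case against.** The strongest reply is that the plan contains no pass rule to criticise. The 1% is introduced as an example, in a sentence that is grammatically broken, and may express an expectation rather than a threshold. Where the protocol wants acceptability limits it states them: Section 9.0 gives 35% and 55% for EPIC bowel change, and 40% and 60% for urinary change. The study is called a pilot and proof of principle, power for toxicities is disclaimed, an interval is promised so readers would see the uncertainty, and no stopping rule or go/no-go step depends on the acceptability sentence.

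Much of this stands, and it rules out several stronger inferences that a reader might draw:
- That the plan allows only 0/12 to pass. This is the most natural reading, but it is one of three, because no cut-off is given.
- That the interval is excluded from the decision. Its role is undefined, not excluded.
- That the plan promises to report toxicity as similar to 1%. The similarity to RTOG 0126 in Section 9.1 is qualified as one of radiation dose.
- That the plan tolerates a regimen ten times as toxic as the benchmark. The 10% rate is an assumption made here.

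The reply does not rescue the sentence itself. A power disclaimer in Section 10.2 and a promised verdict in Section 9.1 contradict each other; the first does not cure the second. Nor does the lack of a cut-off help, since 12 patients cannot support a conclusion against 1% on any of the readings.

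**Conclusion.** The point holds in this form: Section 9.1 promises a safety verdict without a defined criterion, and the sample cannot support a conclusion against the only yardstick supplied. The best possible result, 0/12, leaves rates up to 26.5% compatible with the data, against a benchmark of 1%. The undefined rule alone moves the chance of an acceptable verdict at a 10% true rate from 0% to 65.9%, with 28.2% on the most natural reading.

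The 26.5% and the 368 patients rest only on n = 12, all evaluable, exact binomial limits and the one-sided 97.5% level in Section 9.1. The pass probabilities rest also on the choice of reading and, apart from the 1% column, on assumed true rates. The documents do not support going further and saying that the plan has adopted a zero-event rule.

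**What to change.** In Section 9.1, delete the sentence that deems the profile acceptable and the comparison with 1%. Replace them with text such as:

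> The proportion of patients with acute GI or GU Grade 3+ adverse events will be reported descriptively with its exact one-sided 97.5% upper confidence limit. If no events occur in 12 patients, this limit is 26.5%. No claim will be made that the rate is at or below that of RTOG 0126.

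In the same edit:
- Reconcile the interval with Section 10.2: state one confidence level, whether it is one- or two-sided, and that it is exact.
- Reconcile the acute window between Section 9.1 (30 days) and Section 9.2 (90 days), so that the numerator is fixed before analysis.

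The cost is wording only, with no added patients, visits or procedures. The price is a less favourable safety conclusion: the trial gives up the right to call the acute profile acceptable.

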Standard radiotherapy for the treatment of prostate cancer is delivered at 1.8 to 2 Gy per fraction in a protracted course over 8 to 9 weeks to total doses in the range of 78 to 81 Gy. Following the published work of Hall and Brenner suggesting that prostate cancer may have a lower alpha beta ratio describing the cell line's ability to repair damage caused by ionizing radiation; many centers have routinely adopted into clinical practice that prostate cancer may be treated using larger doses per fraction ranging in size from 3 to 19 Gy in as many as 20 or as few as a single fraction of therapy (Brenner 1999). The assumption is that the alpha beta ratio of most tumors is as high as 10, while the surrounding normal tissues at risk of late radiation reactions is around 3 to 5 (Yoshioka 2013). Positive histopathology findings on co-registered diagnostic MRI data sets (T2 and parametric functional imaging) will be used to segment a dominant biologic target volume and improve disease mapping across the gland. Subjects will then be treated in a series of three SBRT (typically every other day) treatments to deliver a total dose of 29.25 Gy in 9.75 Gy fractions, yielding a total biologic equivalent dose (BED) of 273.15 allowing dose to reach the desired minimal BED of 268 with an assumed alpha beta of 1.2 for prostate cancer as suggested by Martinez (2011). A similar dose regimen has been published by Barkati et.al. using HDR brachytherapy in a three fraction dose escalation trial to deliver minimal dose of 30 Gy in 3 fractions over two days to a maximal dose of 34.5 Gy at 11.5 Gy per fraction. (Barkati 2012). While the published 3 fraction HDR regimen gave a minimal dose of 10 Gy, we feel that 9.75 Gy per fraction is effectively equivalent when taking into account the additional 12 cGy per fraction we will be giving to allow for tracking of intrafraction prostate motion with Image Guided Radiation Therapy using a series of 4 cone beam CT image sessions obtained before, during and after each fraction, thus accounting for a daily fractionated dose of 987 cGy, or 9.9 Gy. What is uniquely novel in this protocol is not the total dose of radiation delivered but rather that it is to be delivered in a non-invasive fashion using SBRT, and more importantly delivered to a novel partial prostate volume using a patented methodology to define the volume at risk to be treated using focal therapy for prostate cancer. This methodology may be adopted as a template for directing therapy to partial organ volumes using other treatment modalities based on the results of this trial if the use of tracked histopathology location is found to have significant influence on the selected treatment volumes in this study beyond what would be used based on functional and anatomic imaging studies alone.

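### Section 9.1 declares the adverse event profile acceptable from acute Grade 3+ events alone; late Grade 3+ events have no criterion and no link to that verdict

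*Combined protocol and SAP*

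**What the plan says.** Section 9.1 defines an acute adverse event as the "first occurrence of worst severity of the adverse event ≤ 30 days after the completion of RT" and a late one as the "first occurrence of worst severity of adverse event > 180 days after RT completion". It then narrows the question: "Specifically, we are interested in the percentage of acute GI and GU Grade 3+ adverse events that may occur". The decision sentence comes next: "If our partial prostate hypofractionated regimen has an acceptable percentage, then it will be deemed to have an acceptable adverse event profile". That sentence does not contain the word acute and gives no number for what is acceptable. The nearest figure is an illustrative 1% acute Grade 3+ rate in the high-dose arm of an earlier cooperative-group trial. On late events, Section 9.1 says only: "Late Grade 3+ GU/GI toxicity information will be collected and reported also".

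Section 10.2 states: "The primary goal of this study is to evaluate acute and late toxicities". It gives acute and late events the same summary, proportions with 95% confidence intervals, and relates GI toxicity to dose-volume histograms. It sets no limit for either.

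Section 9.0 names a different primary goal, mpMRI as a mapping tool. It adds co-primary EPIC bowel and urinary endpoints, described as measures of tolerability and safety. The bowel change runs from baseline to 1 year. Bowel worsening is acceptable in up to 35% of men and unacceptable at 55% or more. For urinary worsening the limits are 40% and 60%.

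Section 9.2 uses another acute window: "All patients will be evaluable for acute toxicity within 90 days from the time of the end of the course of radiation therapy".

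**The concern.** A verdict on the whole adverse event profile should draw on all the events that make up the profile. Here the premise is acute Grade 3+ events and the conclusion carries no such restriction. Read literally, a trial with few early events could report an acceptable profile whatever its late Grade 3+ count. Late rectal and bladder injury is a main safety question for a curative-intent regimen that Section 6.1.1 itself calls novel. Section 19.0 lists acute toxicity and late toxicity as separate publication topics, so the two could be reported at different times, with the unrestricted wording attached to the first.

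**Working it through.** The point is about decision logic, so the main check is to set the passages side by side. The plan has no figure of its own for this rule to reproduce. Its 78% power statement in Section 10.2 concerns a urinary toxicity comparison and has no bearing here.

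**1. What enters each safety criterion**

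| Source | Data | Window | Limit | Feeds the 9.1 verdict? |
|---|---|---|---|---|
| 9.1, acute | Grade 3+ GI/GU | ≤30 days | acceptable, no number | Yes |
| 9.1 and 10.2, late | Grade 3+ GI/GU | >180 days | none | No |
| 9.0, EPIC bowel | worse by more than 5 points | 1 year | 35% / 55% | Not stated |
| 9.0, EPIC urinary | worse by more than 2 points | 1 year is written only beside the bowel score | 40% / 60% | Not stated |

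**2. Size of what is left out.** Inputs: n = 12 treated men (Section 10.2, Sample Size). The documents give no late Grade 3+ rate, so p = 5%, 10% and 20% are assumed. The chance that at least one man is affected is 1 − (1 − p)^12:

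- p = 5%: 1 − 0.95^12 = 1 − 0.540 = 46%; expected 12 × 0.05 = 0.6 men
- p = 10%: 1 − 0.90^12 = 1 − 0.282 = 72%; expected 1.2 men
- p = 20%: 1 − 0.80^12 = 1 − 0.069 = 93%; expected 2.4 men

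**3. Whether the EPIC limits could stand in for a late Grade 3+ limit.** With 12 men, 55% is 6.6, so the bowel result becomes unacceptable at 7 or more. Since 35% is 4.2, it leaves the acceptable range at 5 or more. As an illustration, suppose 20% of men had late Grade 3+ bowel injury and only those men worsened by more than 5 points. Summing C(12,k) × 0.2^k × 0.8^(12−k), the chance of 7 or more is 0.4% and of 5 or more is 7%. If milder worsening were also common, these chances would be higher. The EPIC limits measure something related, but they do not replace a Grade 3+ criterion.

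**4. Whether the acute rule is itself defined.** One event in 12 is 8.3%. If acceptable meant no higher than the 1% example, only 0/12 would pass. That result has probability 0.99^12 = 89% at a true rate of 1%, and still 0.90^12 = 28% at 10%. The one-sided 97.5% upper limit for 0/12 is 1 − 0.025^(1/12) = 26.5%. The plan does not say whether the observed percentage or this limit is to be judged.

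**5. Time windows.** Under Section 9.1, an event whose worst grade first occurs on days 31 to 180 is neither acute nor late. The 3-month visit falls in this gap. Section 9.2's 90-day window covers part of it but contradicts the 30-day definition.

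**The case against.** In context, the decision sentence follows two sentences about acute events, and late events are defined only afterwards. A fair reader could take it to mean an acceptable acute profile, with one word missing. That is plausible, and it is why the remedy is a wording change.

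Late events are not neglected. Adverse events are assessed at every follow-up visit to 24 months, Grade 3+ events are captured and reported under the monitoring plan, and late rates get confidence intervals. No go/no-go decision hangs on the Section 9.1 sentence, and Section 10.2 calls the trial a proof-of-principle study not powered for toxicity. All of this stands and lowers the stakes. A small pilot is still a reason for a narrower conclusion.

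Three stronger readings are tempting, and the documents do not support them:

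- A reader might infer that late injury cannot affect any safety conclusion. The EPIC limits in Section 9.0 are stated safety criteria, and late bowel or urinary injury could breach them. Only the Section 9.1 verdict is closed to late events.
- A reader might infer that the verdict will be issued about a month after the last treatment. No section dates it, and the interim reports described in Section 9.1 cover imaging, workflow and care path.
- A reader might argue from biologically effective dose that the benchmark arm is a poor comparator for acute effects in particular. The protocol calculates that quantity only for tumour, at an alpha/beta of 1.2. The benchmark arm's dose is not given, and an alpha/beta for acutely reacting normal tissue would have to be assumed. This point does not rely on that argument.

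**Conclusion.** The concern holds in limited form. As written, Section 9.1 licenses a conclusion about the whole adverse event profile from acute Grade 3+ GI/GU events alone. No clinician-graded late criterion exists anywhere in the plan, and nothing says what follows if the Section 9.1 verdict and the EPIC limits disagree. The tension with late toxicity as part of the primary goal rests on Section 10.2 only. Section 9.0 states another primary goal, and the two need reconciling. The 46% to 93% range depends on the assumed late rates and shows scale only; the textual finding does not depend on it. This should be corrected before any safety conclusion is reported.

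**What to change.** 1. In the Section 9.1 decision sentence, insert acute (≤30 days after RT) before the words adverse event profile.
2. Add that any overall safety conclusion is drawn only after two things have been assessed: late Grade 3+ GI/GU incidence to 24 months, with an exact confidence interval and against a limit the sponsor prespecifies; and the EPIC bowel and urinary limits in Section 9.0. State how the components combine if they disagree.
3. Give the acceptable acute percentage a number, and say whether the observed rate or its upper confidence limit is compared with it.
4. Reconcile the 30-day and 90-day acute windows, and assign events on days 31 to 180 to a category.
5. Reconcile the primary goals in Sections 9.0 and 10.2.

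The cost is protocol and SAP wording. No new visits or data are needed, since adverse events are already collected to 24 months. The downside is that the overall safety statement waits for those data, while the acute result can still be reported under its own name.
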